EDSS	Expanded Disability Status Scale
EQ-5D	EuroQol 5-Dimension
HAQUAMS	Hamburg Quality of Life in Multiple Sclerosis Scale
HADS	Hospital Anxiety and Depression Scale
HARAS	Hamburg Relapse Assessment Scale
IG	Intervention group
MS	Multiple sclerosis
MMRM	Mixed model for repeated measurements
OR	Odds ratio
PAM	Patient Activation Measure
PBMS	Planned Behaviour in MS Scale
PwMS	People with MS
RCT	Randomised controlled trial
UNDS	United Kingdom Neurological Disability Scale

1 Introduction

This document has been written based on the study protocol version 1.8 dated 29th of November 2021. A design paper was published (Rahn *et al*, 2021). This statistical analysis plan focusses on the evaluation by a randomised controlled trial (RCT). Additionally, a mixed-methods process evaluation and a health economic evaluation will be carried out.

1.1 Background and Rationale

Multiple sclerosis (MS) is a chronic inflammatory, degenerative disease of the central nervous system affecting about 200,000 mostly young people in Germany. MS manifests initially with relapses in about 85% of cases. In Germany, the dominating management approach is an intravenous therapy with high-dose corticosteroids. This is one of the main reasons for hospital admissions of people with MS (PwMS) in Germany.

POWER@MS2 aims to evaluate whether a web-based relapse management programme will positively change relapse management and strengthen autonomy in people with multiple sclerosis.

1.2 Objectives and Endpoints

POWER@MS2 investigates the hypothesis that the web- and evidence-based relapse management programme results in more autonomous relapse treatment decision-making by PwMS.

Clinical endpoints are evaluated by the trial statistician, while endpoints related to health economic aspects of the trial are evaluated by the Health Economics team and therefore not specified in this SAP. Primary, secondary and safety endpoints are listed in Table 1.

Table 1 Objectives and related endpoints

	Objective	Endpoint
Primary	To determine whether the programme leads to a decrease in corticosteroid relapse treatment and less intravenous administered corticosteroids in case of steroid treatment.	Proportion of relapses not treated or treated with oral corticosteroids during the follow-up.
Secondary	To determine whether the programme results in more autonomous relapse treatment decisions.	Differences in decision autonomy measured by CPS.
	To determine whether the programme leads to fewer relapses.	Annualised relapse rate.
	To determine whether the programme leads to an increase in risk-knowledge.	Changes in Risk Knowledge.
	To determine whether the programme leads to more empowerment.	Changes in empowerment measured by PAM from baseline to end of study.

	To determine whether the programme leads to a more autonomous steroid treatment decision-making	Changes in PBMS relapses.
Safety	Assessment of safety of the intervention	Changes in HAQUAMS. Changes in HADS. Changes in EDSS. Changes in UNDS.

1.3 Primary objective and endpoint

To determine the impact of the programme on corticosteroid treatment decision in case of a relapse, the proportion of relapses and their treatment with oral corticosteroids is assessed. Two experienced, blinded neurologists will independently rate all relapses at end of study as definite, possible or no relapses based on the information assessed in the 3-monthly telephone interviews.

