1.4 Secondary objective and endpoint

Secondary endpoints are recorded as listed in Table 1. The annualised relapse rate is calculated based on the standardised assessment of relapses during the 3-monthly phone interviews. For further details, see Section 5.1.

2 Study methods

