2.1 Trial design

Power@MS2 is a national, parallel group, superiority, investigator and participant blinded RCT. Participants will be randomized to the web-based programme (intervention group, IG) or a standard information on relapse management programme (control group, CG).

Participating physicians and MS centres will not be provided with any information about group assignments. Furthermore, outcome assessors are blinded. Blinding of the participants is pursued, but only to a limited extent. It cannot be prevented that patients discuss the intervention contents with their physician and might realise the group assignment.

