3.3 Analysis populations

Primary analysis is planned following the intention-to-treat principle. The intention-to-treat population contains all randomised patients. For the primary endpoint, only definite and possible relapses are considered.

4 Trial population

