5.1 Outcome definitions

A full list of outcomes and their timing is described in Section 2.7.

Ten adapted items of the **Patient Activation Measure (PAM13)** are used to assess empowerment (Zill, 2013). The items of the PAM13 range from 1 (Disagree at all) to 4 (Fully agree). The raw score is the sum of the items divided by the number of answered questions (excepting non-applicable items) and multiplied with 10. Afterwards the raw score is transformed to a range from 0 to 100 (Moljord, 2015).

$$\text{10-item PAM calculation expressed as formula: } 100 \times \frac{\left(\frac{\text{sum score}}{\text{Number of answered questions}} \times 10 \right) - 10}{(40-10)}.$$

An adapted empowerment scale with three of the five items from Bann *et al* (2010) was used to assess empowerment. The items are answered on the 3-point scale: "no," "yes, a little," or "yes, a lot."

Control Preference Scale (CPS) is used to assess preferred and realised role preference in steroid treatment decision-making. It consists of five roles ranging from A (the individual making the treatment decisions), over C (the individual making the decisions jointly with the physician) to E (the physician making the decisions). Satisfaction with the decision will be measured in a telephone interview within 3 months in case a decision for or against steroid treatment has been made.

Hamburg Quality of Life in MS Scale Version 10.0 (HAQUAMS) is a questionnaire for measuring quality of life in PwMS (Gold *et al.*, 2001). It consists of 44 items with mostly 5-point-likert scale. Twenty-eight of the items are subdivided into the six subscales:

- Fatigue: Items 6, 7, 8, 9
- Cognition: Items 10, 11, 12, 13
- Lower extremity: Items 17, 18, 19, 20
- Upper extremity: Items 21, 22, 23, 24, 25
- Communication: Items 29, 30, 31, 32, 33, 34
- Mood: Items 36, 37, 38, 39, 40.

Mean subscale scores are calculated, the total score is built by calculating the mean of the subscale score means: *HAQUAMS total score = mean(mean(upper extremity), mean(lower extremity), mean(fatigue), mean(cognition), mean(communication), mean(mood))*. Subscale and total score range from one to five; high scores indicate low quality of life. For missing items, mean substitution is allowed.

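### Relapses are rated from telephone-interview information that is not restricted to exclude steroid treatment, so entry into the primary denominator can depend on the primary outcome

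*SAP*

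**What the plan says.** The primary endpoint (SAP 1.2, Table 1) is the "Proportion of relapses not treated or treated with oral corticosteroids during the follow-up". Its unit of analysis is the relapse (2.3).

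Whether an episode counts is decided by rating. Two blinded neurologists, working independently, "rate all relapses at end of study as definite, possible or no relapses based on the information assessed in the 3-monthly telephone interviews" (1.3). Section 3.3 then states: "For the primary endpoint, only definite and possible relapses are considered". An episode rated as no relapse leaves the analysis.

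The telephone contacts also carry content on treatment decisions. Section 5.1 says that satisfaction with the decision is "measured in a telephone interview within 3 months in case a decision for or against steroid treatment has been made". Table 2 in section 2.7 schedules relapse history, relapse questions, and decision autonomy and satisfaction at the same three-monthly time points.

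On masking, section 2.1 says "Furthermore, outcome assessors are blinded", in a paragraph about who may learn the group assignment. The SAP does not mention masking the raters to steroid use or route.

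**The concern.** Being unaware of the group stops a rater from favouring an arm directly. It does not stop a rater who can see that an episode was treated intravenously from being readier to call it a relapse than one that went untreated. If that happens, selection into the primary analysis depends on the outcome being analysed. Because the programme aims to change treatment, the mix of untreated, oral and intravenous episodes is expected to differ between arms, and the selection need not cancel out.

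The rating leaves room for this. At the blinded review (2.3), 20 events were definite and 51 were definite or possible. So 31 of 51 (61%) were only possible, and the boundary that matters for inclusion lies between possible and no relapse.

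The primary odds ratio, the reported percentages and the number of analysable relapses are at stake.

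**Working it through.** **Plan's own figure.** Inputs from 2.3: 78% vs 56%, two-sided 5%, power 85%. With pooled variance under the null and no continuity correction:

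n = [1.960·√(2·0.67·0.33) + 1.036·√(0.78·0.22 + 0.56·0.44)]² / 0.22² = (1.303 + 0.670)² / 0.0484 ≈ 80.5, so 81 per group. This matches the SAP; power at 81 is 85.2%. The planned odds ratio is (0.78/0.22)/(0.56/0.44) = 2.79.

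**Effect of treatment-dependent rating.** In each arm let u, o and v be the true shares of untreated, oral and intravenous relapses. Let r be the probability that an untreated episode is accepted as definite or possible, relative to a steroid-treated one, with the same r in both arms. The observed odds are (o + r·u)/v. With w = u/(u + o), the untreated share of non-intravenous relapses:

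OR observed = OR true × [1 − (1 − r)·w(IG)] / [1 − (1 − r)·w(CG)].

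The direction therefore depends only on which arm has the larger w. The SAP gives neither r nor the untreated/oral split, so everything below is assumed. Each split is chosen to keep 78% vs 56%, with CG 20/36/44 (untreated/oral/intravenous) in A and B.

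*A. Shift to no treatment.* IG 42/36/22; w = 0.538 vs 0.357. Acceptance is 0.95 if steroid-treated and 0.8, 0.7 or 0.6 if untreated (r = 0.842, 0.737, 0.632).

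| Untreated accepted | IG vs CG | Difference, points | OR | Kept fraction IG / CG |
|---|---|---|---|---|
| 0.8 | 76.4% vs 54.6% | 21.9 | 2.70 | 0.887 / 0.920 = 0.96 |
| 0.7 | 75.3% vs 53.6% | 21.7 | 2.64 | 0.845 / 0.900 = 0.94 |
| 0.6 | 74.0% vs 52.5% | 21.5 | 2.57 | 0.803 / 0.880 = 0.91 |

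With 81 rated relapses per arm, power is 84.0%, 82.9% and 81.5%. If 81 is the number before rating, counting the steroid-treated episodes as all kept, it is 82.1%, 79.5% and 76.4%. These figures ignore clustering within patients.

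*B. Shift from intravenous to oral.* IG 20/58/22; w = 0.256 vs 0.357. For r = 0.8, 0.6 and 0.5 the OR is (0.74/0.22)/(0.52/0.44) = 2.85, (0.70/0.22)/(0.48/0.44) = 2.92 and (0.68/0.22)/(0.46/0.44) = 2.96. The same fraction is removed from each arm. At the three r values of scenario A the OR is 2.83, 2.87 and 2.90, so the opposite direction comes from the split and not from a different r.

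*C. Equal w in both arms.* IG 39/39/22, CG 28/28/44; w = 0.5 in each. The OR stays at 2.79 for every r, although both percentages fall (76.1% vs 53.4% at r = 0.8).

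*D. No true effect on the endpoint.* 56% in both arms, but untreated 56% in IG and 28% in CG. The observed difference is −2.9 points at r = 0.8 (50.5% vs 53.4%) and −9.9 points at r = 0.5 (38.9% vs 48.8%).

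**The case against.** **The premise is an inference.** No sentence says that the raters receive steroid use or route. Table 2 lists relapse questions and decision items on separate rows, and 5.1 concerns satisfaction with a decision, not the raters' material. A protocol or rating manual that is not at hand may mask treatment. This stands as a limit. It does not remove the point, because 1.3 itself fixes the source of the rating and does so without restriction.

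**A reader might infer that the bias runs towards no effect and that more episodes are lost from the intervention group.** The document does not support this. It holds in scenario A only because the oral share is kept at 36% in both arms. The primary objective in Table 1 covers both less steroid treatment and less intravenous use among those treated, so a shift to oral is equally intended. Under that shift the OR rises and removal is equal.

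**A reader might also infer that the annualised relapse rate would favour the programme.** Section 1.4 says "The annualised relapse rate is calculated based on the standardised assessment of relapses during the 3-monthly phone interviews" and does not mention the neurologists' ratings. The kept-fraction ratios of 0.91–0.96 in scenario A would matter only if the ratings feed that rate.

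**The effect is modest, and the inclusive threshold helps.** In scenario A the difference moves by half a point at most, and counting possible relapses limits exclusion to episodes rated as no relapse. Both are fair. Larger distortions need stronger assumptions, as in D at r = 0.5.

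**Conclusion.** The point holds as a weakness in how the rating is specified, not as a demonstrated bias. The text allows the decision on who enters the primary denominator to be made with sight of the primary outcome, and group blinding does not prevent that. The size and direction are unknown. Under the assumed splits and acceptance probabilities the OR of 2.79 could fall to 2.57–2.70, rise to 2.85–2.96, or stay where it is. That intravenously treated episodes are more readily accepted is itself an assumption without a source in the SAP. The change is worth making because it is cheap and removes the dependence whichever way it would run.

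**What to change.** In section 1.3, state that the raters receive the interview data on symptoms, onset, duration and severity only. Steroid use, route, admission for treatment, decision role and satisfaction are removed, so that raters are masked to treatment as well as to group. In section 5.2 or 5.4, add a sensitivity analysis of the primary endpoint on all reported episodes regardless of rating.

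The cost is a sentence, a filtered listing and one further model run, with no extra visits. The downside is that raters lose treatment as a clue to severity. Any ratings already made with treatment visible, possibly including those behind the counts in 2.3, would need repeating from the masked listing. If treatment is already masked, a sentence in 1.3 confirming it settles the matter.

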1.4 Secondary objective and endpoint

Secondary endpoints are recorded as listed in Table 1. The annualised relapse rate is calculated based on the standardised assessment of relapses during the 3-monthly phone interviews. For further details, see Section 5.1.

2 Study methods

2.1 Trial design

Power@MS2 is a national, parallel group, superiority, investigator and participant blinded RCT. Participants will be randomized to the web-based programme (intervention group, IG) or a standard information on relapse management programme (control group, CG).

Participating physicians and MS centres will not be provided with any information about group assignments. Furthermore, outcome assessors are blinded. Blinding of the participants is pursued, but only to a limited extent. It cannot be prevented that patients discuss the intervention contents with their physician and might realise the group assignment.

2.2 Randomization

PwMS are randomized in a 1:1 allocation ratio to IG or CG stratified by the centre using block randomization through a computer-generated system in secuTrial®.

2.3 Sample Size

The unit of analysis for the primary endpoint is the occurrence of relapses. Eighty-one relapses per group yield in a power of 85% at two-sided significance level of 5% given proportions of 78% and 56% of orally treated or non-treated relapses in IG and CG. It is expected that this relapse rate can be observed in 170 PwMS with 1 to 2 years follow-up, corresponding to an annual rate of 0.64. The dropout rate is expected to be at 10%. Therefore, 188 PwMS will be randomized.

The blinded sample size recalculation report based on a blinded data export from 10th of September 2021 comprising events of 107 patients at that time with 51 possible and definite relapses ([name], [name] and [name], 2021).

In the first definition of the primary endpoint events, only definite relapses were counted. In the second definition, possible relapses were counted additionally. The first definition resulted in 20 primary endpoint events, while the second resulted in 51 primary endpoint events.

According to the estimated relapse rate per year of 0.8775 (95%-CI: [0.6632, 1.1612]), 125 PwMS need to be followed up for two years. Until 20th of October 2021, 92 patient-years were observed and 58 patient-years documented. With an extension of recruitment for further 3 months and flexible follow-up, the goal of 250 patient-years can be reached. Based on the inclusion of further 39 patients and assuming no change in drop-out rate, 294.3 patient-years can be reached, but only 277 years will be documented as documentation is performed every three months. Therefore, 146 PwMS should be sufficient to reach a power of 85%.

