5.2 Analysis methods

In the analysis of primary and secondary endpoints, centres with less than 10 patients are pooled into one centre.

The primary endpoint is analysed using a generalised linear model with mixed effects and logit link function. Subject-specific effects are modelled as random effects, while intervention group and study centre are included as fixed effects. In case of nonconvergence due to a flat likelihood in the variance of the subject-specific effects near 0, the model will be simplified by removing the random subject-specific effects resulting in a generalized linear model (logistic regression). In this case correction of standard errors by using generalized estimating equations (GEE) will be explored. The intervention effect is reported as odds ratio (OR) with 95% CI and p-value testing the null hypothesis of no intervention effect ($H_0: OR = 1$).

```
library(MASS)

prim.mod <- glmer(oral_treated ~ intervention + site + (1|Patient.Id),
                  data = primEnd, family = binomial(link = "logit"))
summary(prim.mod)
emmeans(prim.mod ~ intervention, type = "response")
```

Longitudinal assessments of the quality of life and impairment are analysed employing Gaussian linear models for repeated measures with intervention group, time, intervention-by-time interaction and study centre as factors and, if the instrument was assessed at baseline, its baseline score as a covariate (mixed model for repeated measurements, MMRM).

The error terms are assumed to follow a multivariate normal distribution with unstructured covariance matrix. Least squares mean changes from baseline will be reported for both groups with 95% CI as well as the difference between the least-squares intervention group means with 95% CI and p-value testing the null hypothesis of no treatment effect ($H_0: \delta = 0$).

```
library(lme4)
library(car)
library(emmeans)

var_sec <- lmer(var ~ baseline_var + intervention + time + intervention * time +
                  site + (1|Patient.Id), data = secEndpoints)
summary(var_sec)
res <- Anova(var_sec, type = "III", test.statistic = "F")
res

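### The 85% power at 81 relapses per group assumes independent relapses, the 250 patient-years do not follow from the rate they are attributed to, and the 109-relapse end rule fits neither total

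*SAP*

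**What the plan says.** Section 2.3 of the SAP takes the relapse as the planning unit ("The unit of analysis for the primary endpoint is the occurrence of relapses") and states the target: "Eighty-one relapses per group yield in a power of 85% at two-sided significance level of 5" percent, "given proportions of 78% and 56% of orally treated or non-treated relapses in IG and CG". It expects these relapses "in 170 PwMS with 1 to 2 years follow-up, corresponding to an annual rate of 0.64". It mentions no within-patient correlation or design effect.

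Randomisation is by patient (section 2.2: "PwMS are randomized in a 1:1 allocation ratio to IG or CG"). The primary model in section 5.2 is a mixed logistic regression for relapses in which "Subject-specific effects are modelled as random effects". The random effect is removed only if the fit fails because its variance is close to zero, and GEE standard errors are then to be explored.

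The blinded recalculation in section 2.3 starts from an estimated rate of 0.8775 per year (95% CI 0.6632 to 1.1612) and concludes that "125 PwMS need to be followed up for two years". This becomes a goal of 250 patient-years. With 146 patients it projects 277 documented patient-years and again claims 85% power.

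Section 2.7 ends the trial at 109 documented relapses, or once 125 patients have 24 months of follow-up.

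**The concern.** Three figures in the plan should connect and do not.

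- **The 85% has no allowance for clustering.** The endpoint is how a relapse is treated, and one patient may decide several times. The primary model expects such decisions to be alike within a patient. A power figure for independent relapses is then the most favourable value, not the expected one.
- **The 250 patient-years do not follow from 0.8775 and 162 relapses.** The text presents them as if they did. Without the relapse target or the rate really used, the closing claim of 85% power with 146 patients cannot be checked from the SAP.
- **The number that can end the trial, 109, does not appear in section 2.3.** If it is a total, stopping there would leave the trial well short of the stated power.

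**Working it through.** **Inputs from the SAP.** Proportions 0.78 and 0.56, two-sided 5%, 81 relapses per group (162 in total); 170 patients; rates 0.64 (original) and 0.8775 (re-estimated, lower CI limit 0.6632); 125 patients for 2 years; 146 patients with 277 documented patient-years (all section 2.3); 109 relapses (section 2.7).

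**1. Reproducing 81 per group.** The pooled two-proportion formula for independent observations is

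n = [1.960 × √(2 × 0.67 × 0.33) + 1.036 × √(0.78 × 0.22 + 0.56 × 0.44)]² / 0.22² = 80.5, rounded up to 81.

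Power is 85.2% at 81 and 84.8% at 80. The stated figure is reproduced, with nothing in reserve beyond rounding.

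**2. Adding within-patient correlation to the original plan.** The ICC is an assumption, because the SAP gives none. For Poisson relapse counts with mean m per patient, the design effect is DE = 1 + m × ICC. Here m = 162/170 = 0.953, and the effective number per group is 81/DE.

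| Assumed ICC | DE | Effective n per group | Power | Total relapses for 85% (162 × DE) |
|---|---|---|---|---|
| 0 | 1.00 | 81.0 | 85.2% | 162 |
| 0.05 | 1.05 | 77.3 | 83.6% | 170 |
| 0.1 | 1.10 | 74.0 | 81.9% | 177 |
| 0.2 | 1.19 | 68.0 | 78.5% | 193 |
| 0.3 | 1.29 | 63.0 | 75.3% | 208 |

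Power drops below 85% once DE exceeds 81/80.46 = 1.007, that is, at an ICC of about 0.007/0.953 = 0.007.

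**3. From the rate to 250 patient-years.**

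- At 0.8775: 162/0.8775 = 184.6 patient-years, or about 92 patients for two years. Conversely, 250 × 0.8775 = 219 relapses, 35% more than 162.
- At the lower CI limit: 162/0.6632 = 244 patient-years, or about 122 patients for two years.
- At the original rate: 162/0.64 = 253 patient-years.

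The last two come close to 250. The rate named in the sentence does not.

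**4. Power of the recalculated trial (146 patients, 277 documented patient-years).** The ICC at which 85% is just kept is (relapses/162 − 1)/m.

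- At 0.8775: 277 × 0.8775 = 243 relapses, m = 243/146 = 1.665, limit (1.500 − 1)/1.665 = 0.30.
- At 0.6632: 277 × 0.6632 = 184 relapses, m = 184/146 = 1.258, limit (1.134 − 1)/1.258 = 0.11.

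**5. The end rule.** As a total, 109 relapses are 54.5 per group, with 69.0% power under independence. As a per-group number they give 93.8%. The figure matches neither 162 nor 219 as a total. It is close to half of 219, and equally close to 125 × 0.8775 × 1 year = 109.7, so arithmetic alone does not show what was meant.

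**The case against.** The strongest reply is that no loss of power is shown. The ICC is unknown, section 5.2 itself foresees a patient variance near zero, and at an ICC of 0.05 the original plan loses under two points. The primary analysis models the patient effect, so inference is protected and only the planning text is affected. The recalculated trial collects more relapses than 162 at the quoted rate. The recalculation report that the SAP cites is not at hand and may contain the derivation.

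Most of this stands, and it limits the point. A reader might infer that 162 relapses certainly miss 85%. The SAP does not support that without an ICC: at zero the figure is exact. A reader might also combine 162 relapses with the 1.755 relapses per patient expected over two years at 0.8775 and obtain a larger loss. That would be about 92 patients, a trial that the SAP does not plan.

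Another tempting inference is that 250 patient-years rest on an ICC of 0.20, because 162 × (1 + 1.755 × 0.20) = 219. The lower CI limit and the original rate nearly reproduce 250 with no design effect at all, so 0.20 cannot be read as the sponsor's assumption, nor 219 as its target.

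The reply does not rescue the text as written. Section 2.3 attributes 125 patients to 0.8775, which does not give that number from 162 relapses, and nothing in the SAP links 109 to either total.

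**Conclusion.** The point holds in a limited form. The 85% at 81 relapses per group is a best case that requires an ICC of essentially zero, while the primary model allows for correlation. For the original plan the cost is about 2, 3, 7 and 10 percentage points at an ICC of 0.05, 0.1, 0.2 and 0.3. These values rest on an assumed ICC and Poisson relapse counts.

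The basis of the 250 patient-years is not the one that the sentence names. It is unstated, and the patient-year goal itself is not shown to be wrong. The recalculated trial may well have enough relapses: its margin reaches an ICC of about 0.3 at a rate of 0.8775, but only about 0.1 at 0.6632.

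The 109-relapse rule has the most direct consequence, because read as a total it allows the trial to end with 69% power before any clustering is counted. The SAP should be corrected on all three points.

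**What to change.** - In section 2.3, label 81 per group (162 in total) as the figure for independent relapses, and give its power as a range over an assumed ICC, with the assumption on relapse counts stated.
- Correct the sentence on 125 patients so that it names the rate and the total relapse target actually used, with any design effect. Take these from the recalculation report. Do not enter an ICC of 0.20 or a target of 219 unless that report contains them.
- Restate the power of the recalculated trial: with 277 documented patient-years, at least 85% up to an ICC of about 0.3 at 0.8775, and up to about 0.1 at 0.6632.
- In section 2.7, say whether 109 relapses is a total or a per-group number, and reconcile it with the target in section 2.3.

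The cost is SAP wording. The power quoted for 162 relapses becomes less favourable. No extra patients are requested.
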